The sample size for this study is calculated using G-power 3.1.9.7 statistical software to determine the effect size. According to Cohen (1988), effect sizes are categorized as large (0.80), medium (0.50), and small (0.20). Since most research results have an effect size of 0.50, this study sets the criterion of at least a medium effect size. With α =0.05, statistical power (power)=0.80, and effect size set at 0.5, the estimated sample size is 60 individuals. Considering potential changes in the elderly or refusal to participate, a dropout rate of 15% is estimated. Therefore, a total of 70 elderly individuals from community-based activities will be recruited for this study. The inclusion criteria for this study are as follows: (1) aged 65 and above, (2) able to communicate in Mandarin or Taiwanese and willing to complete interviews or self-administered questionnaires, (3) no mobility impairments (e.g., stroke, Parkinson's disease, motor neuron diseases), (4) no severe cardiovascular diseases, (5) no degenerative joint diseases or acute attacks in the past three months, (6) lower limb joint surgery performed more than three months ago, and (7) no dizziness or any unstable health conditions that hinder exercise. During the study period, participants who do not engage in physical

activity for more than three weeks or have missing pre-test or post-test data will be excluded from the statistical analysis.

Ethical Considerations:

Prior to conducting the study, the research proposal will be submitted to the Institutional Review Board (IRB) for review and approval. Approval was obtained from the Taipei Medical University Joint Institutional Review Board (TMU-JIRB) on November 24, 2022, with the approval letter numbered N202210004 (see Appendix 1). This study aims to investigate the effects of VR interactive games as part of exercise prescriptions on the balance function and lower limb strength of elderly participants.

Section 3: Intervention Tools

Hardware Setup:

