After data collection, the collected data will be coded, documented, and analyzed using the Statistical Package for the Social Sciences (SPSS) 19.0 Chinese version software. Both descriptive and inferential statistics will be employed. A significance level of p < .05 will be used to determine statistical significance.

1. Descriptive Statistics:

Categorical variables of demographic data for both experimental and control groups will be presented as percentages, while continuous variables will be described using means and standard deviations.

2. Inferential Statistics:

(a) Independent t-test or Mann-Whitney U test:

Analyze the differences between the experimental and control groups in variables such as balance function, muscle strength, flexibility, cardiovascular capacity, and quality of life befor intervention. A Shapiro-Wilk test will be conducted to check for normal distribution. If the data is normally distributed, an independent t-test will be used; otherwise, the Mann-Whitney U test will be employed.

(b) Chi-Squared Test:

Analyze the homogeneity of basic demographic characteristics (age, gender, education level, marital status), exercise habits, duration of each exercise session, and experience of falling in the past year between the two groups.

(c) Dependent Samples t-test or Wilcoxon Signed Rank Test: Analyze the differences in variables such as balance function, muscle strength, flexibility, cardiovascular capacity, and quality of life within each group 之前 and after the intervention. A Shapiro-Wilk test will be conducted to check for normal distribution. If the data is normally distributed, a dependent samples t-test will be used; otherwise, the Wilcoxon signed rank test will be employed.

(d) ANCOVA Analysis using Intention-to-Treat Analysis:

ANCOVA will be employed to compare the post-test scores between the experimental and control groups while controlling for pre-test scores. This analysis will utilize intention-to-treat principles.

[figure not shown]

Figure 8. Flowchart of the application of virtual reality interactive games

to the lower limb balance of community elders

Research Results

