This study involved the intervention of the experimental group using virtual reality interactive games, while the control group underwent exercise interventions led by original instructors. Both groups participated in modal rate-intensity sessions three times a week for 12 weeks, totaling 36 sessions. Testing was conducted befor and three months after the completion of the program. A total of 84 participants were recruited from two community care activity centers in Taipei City, but 14 participants were excluded due to personal reasons or inability to consistently monitor data due to illness. Ultimately, data from 70 participants who completed at least 30 sessions were analyzed.

Regarding participant attrition, the experimental group initially recruited 35 participants. However, during the 12-week, 36-session program, five participants were absent for over one-third of the sessions (12 sessions) due to health issues or personal preferences, rendering their data unusable. The experimental group experienced a dropout rate of 14.28%. The control group initially recruited 35 participants, but only 33 completed the post-intervention assessment. Two participants were excluded from the analysis due to absence for over one-third of the sessions. The dropout rate for the control group was 8.57%. Both groups had dropout rates within the predetermined range of 15% set befor the study.

The study spanned 36 sessions from February 13th to May 31st, [insert year]. Data from participants who attended less than 12 sessions were

excluded from statistical analysis. Thus, statistical analysis was conducted on data from 30 participants in the experimental group and 33 participants in the control group.

Section 1: Participant Demographics

This study recruited a total of 70 participants, with 35 participants in both the experimental and control groups. Among them, 63 participants completed the entire study, with 30 participants in the experimental group and 33 participants in the control group. The average age of the experimental group (30 participants) was 77.7 years, with the majority being female (96.7%) and married (90.0%). See Table 4-1 for details. Assessment of demographic data in both groups showed no significant differences. Independent samples t-tests or Mann-Whitney U tests and chi-squared tests were used to analyze demographic data, revealing no significant differences between the two groups' demographic characteristics, as shown in Table 2.

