less than 30 minutes	0 (0%)	3 (9.1%)	
more than 30 inutes	22 (73.3%)	15 (45.5%)	
30-60 minutes	8 (26.7%)	15 (45.5%)	
Falls experience in the past			1.034 (0.669)
year			
No falls	23 (76.7%)	25 (75.8%)	
≤3 次	6 (20.0%)	5 (15.2%)	
>3 次	1 (3.3%)	3 (9.1%)	

Table 3 Descriptive Statistics

Section 2: Comparison of Functional Fitness

1. Analysis of Demographic Data

Before the intervention of virtual reality interactive gaming, the participants' functional fitness, including height, weight, lower limb muscle endurance, lower limb flexibility, and agility, were assessed descriptively.

In the pre-test assessment, there were no significant differences between the experimental group and the control group in terms of fitness and quality of life, as indicated by independent samples t-tests, as shown in Table 4.

2. Comparison of Pre-test and Post-test within the Experimental and Control Groups

The results of dependent samples t-tests (Table 5) showed statistically significant improvements in four assessment outcomes in the experimental group, including the 2-minute step test (p < 0.001), left and right chair sit and reach (p < 0.001, p = 0.003), and psychological quality of life (p = 0.008).

In the control group, there was a statistically significant improvement in one assessment outcome, the 30-second chair stand test (p = 0.001).

	Test group (N=30)	Control group	t value (p) or
		(N=33)	Z value (p)
pretest assessment			
BMI	27.0 ± 3.5	25.4 ± 3.8	1.77 (0.077) §
30 seconds sit and stand	16.3±4.6	17.7±5.2	-1.19 (0.234) §
2 minutes to step	96.0±20.7	92.5±25.4	0.60 (0.548)
The seat body bends forward (right)	2.9±10.1	2.6±12.0	0.25 (0.799) §
The seat body bends forward (left)	1.2±11.2	1.4±13.4	-0.08 (0.935)‡
Get up and walk Around at 2.4 meters	8.5±3.2	8.4±3.6	0.70 (0.483) §
Physiological quality of life	10.8±1.4	11.4±1.5	-1.75 (0.086)‡
Psychological quality of life	11.1±1.8	11.7±1.8	-1.28 (0.200) §
Quality of social life	11.2±1.9	11.4±1.1	-0.652 (0.515)§
Environment quality of life	10.6±2.2	10.3±2.0	0.090 (0.928) §

Table 4Functional fitness pre-test of the experimental group and the

control group

[‡] Using independent sample t test

§Using the Mann-Whitney U test

Table 5 Intra-group pre- and post-test comparison between the

experimental group and the control group

		Test g	roup (N=30))		Control	group (N=33	3)
			score				score	

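### Table 5: the printed pre- and post-test means do not give the printed mean change for 2-minute step and left sit-and-reach, two of the three fitness endpoints claimed as benefits

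*Combined protocol and SAP*

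**What the plan says.** Chapter 3, Section 2 (Research Participants) states that people who "have missing pre-test or post-test data will be excluded from the statistical analysis". The opening of Chapter 4 says "statistical analysis was conducted on data from 30 participants in the experimental group and 33 participants in the control group", and Table 5 carries one N per arm, 30 and 33. Chapter 3, Section 6 sets the threshold: "A significance level of p < .05 will be used to determine statistical significance".

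Chapter 4, Section 2, item 2 summarises Table 5. The experimental (VR) group is said to have improved on the step test, both sit-and-reach tests and psychological quality of life. For the other arm it says "In the control group, there was a statistically significant improvement in one assessment outcome, the 30-second chair stand test (p = 0.001"). Item 3 and Table 6 then claim a between-group benefit by ANCOVA on three fitness endpoints: 2-minute step (p < 0.001), right sit-and-reach (p = 0.010) and left sit-and-reach (p = 0.002). The Abstract repeats these p-values.

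**The concern.** When every analysed person has both measurements, the mean of the paired changes must equal the difference of the two means, apart from rounding. Table 5 breaks this for step and left sit-and-reach in both arms, and no text explains why.

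At stake are the size of the benefit a reader would take from these endpoints and the statement about the control arm. Whichever column is wrong, a published figure for two claimed benefits is wrong: either the post-test mean, which is the variable the ANCOVA compares, or the change and its paired test.

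**Working it through.** **Matching rows.** The row labels in Table 5, as the text reads, are offset from the values, possibly through PDF extraction. I matched rows by the Table 4 pre-test values: "2 minutes to step" is 96.0 (VR) and 92.5 (control); "The seat body bends forward (left") is 1.2 and 1.4. The arithmetic does not depend on the labels.

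**Means against printed change.** Improvement = post-test minus pre-test. Rounding allows ±0.10 where both means have one decimal, ±0.55 for step (post-test means are whole numbers), and ±0.05 on the printed change.

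| Row | Pre | Post | Post − pre (range) | Printed change |
|---|---|---|---|---|
| Step, VR | 96.0 | 121 | 25.0 (24.45 to 25.55) | 26.6 |
| Step, control | 92.5 | 98 | 5.5 (4.95 to 6.05) | 3.8 |
| Left, VR | 1.2 | 5.9 | 4.7 (4.6 to 4.8) | 4.9 |
| Left, control | 1.4 | 2.9 | 1.5 (1.4 to 1.6) | 0.2 |

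All four fail; VR left fails by only 0.05 (4.80 against a minimum of 4.85). Right sit-and-reach reconciles exactly in both arms (4.4 and 0.3).

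**Reproducing the printed tests.** Paired t = change / (SD / √n).
- Step, VR: 26.6 / (31.2/√30) = 4.67 (printed 4.67).
- Step, control: 3.8 / (15.0/√33) = 1.46 (printed 1.47).
- Left, VR: 4.9 / (8.1/√30) = 3.31 (printed 3.29).
- Left, control: 0.2 / (1.5/√33) = 0.77 (printed 0.79).

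Change, SD, t and p therefore agree with each other. These rows are footnoted as Wilcoxon tests but reproduce as paired t tests.

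**Could missing pairs explain it?** Implied n = (t × SD / change)². Over rounding this is 29.7 to 30.3 for VR step, 32.4 to 35.0 for control step and 28.5 to 30.7 for VR left. Control left (20.7 to 67.5) is uninformative. From Table 6, error df = F(1 − η²)/η²:
- Step: 21.154 × 0.733/0.267 = 58.1.
- Left: 10.294 × 0.849/0.151 = 57.9.

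That fits 63 participants less five parameters (intercept, group, age, pre-test, and education as a single term, which is my assumption).

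**Which column fits Table 6?** I rebuilt an ANCOVA adjusted for pre-test only, taking the printed SDs as correct; age and education cannot be included. The covariance in each arm is (s₁² + s₂² − s_change²)/2, and the pooled slope is b. The adjusted difference is the difference in change plus (1 − b) times the pre-test difference. F = (adjusted difference / SE)².

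| Endpoint | b | SE | Source of change | Adjusted difference | F | Table 6 F |
|---|---|---|---|---|---|---|
| Left | 0.834 | 1.350 | printed changes | 4.67 | 12.0 | 10.294 |
| Left | 0.834 | 1.350 | printed means | 3.17 | 5.5 (p = 0.022) | 10.294 |
| Step | 0.451 | 5.213 | printed changes | 24.72 | 22.5 | 21.154 |
| Step | 0.451 | 5.213 | printed means | 21.42 | 16.9 | 21.154 |
| Right | 0.875 | 1.351 | both agree | 4.14 | 9.4 | 7.091 |

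The printed changes lie closer to Table 6 for both endpoints. For right sit-and-reach, where nothing is in dispute, the reported F is lower than the rebuilt one. For the left-side means to be right, the extra covariates would have to nearly double F.

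**If the means were right.** This keeps the printed change SDs and uses two-sided tests (the plan does not state sidedness).
- Control left: 1.5 / (1.5/√33) = 5.74, p < 0.001 (printed p = 0.433).
- Control step: 5.5 / (15.0/√33) = 2.11, p = 0.043, with range 0.027 to 0.068 over rounding (printed p = 0.151). It loses significance if the SD exceeds about 15.5.
- Between-arm difference, left: 4.9 − 0.2 = 4.7 becomes 4.7 − 1.5 = 3.2. Welch SE = √(8.1²/30 + 1.5²/33) = 1.50; p goes from 0.004 to 0.041.
- Between-arm difference, step: 26.6 − 3.8 = 22.8 becomes 25.0 − 5.5 = 19.5. SE = √(31.2²/30 + 15.0²/33) = 6.27; p goes from 0.0008 to 0.003.

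**The case against.** The strongest reply is that this is a transcription fault in the post-test means and leaves the analysis untouched. The pre-test means recur in Table 4. The changes are backed by their own SD, t and p, and by Table 6. Nothing corroborates the post-test means: both step values have lost their decimal, and the control left value of 2.9 repeats the control right value in the row above. Moreover, the benefit claim rests on the ANCOVA and not on the within-group tests.

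Most of this stands, and it makes the post-test means the likelier fault. It is not proof. The rebuilt ANCOVA omits two covariates and relies on the printed SDs. The reply also concedes that printed figures for two claimed benefits are wrong.

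Two stronger readings are tempting. A reader might infer that the mismatch decides whether controls also improved, so that they improved on three outcomes and not one. That inference combines a change taken from the means with an SD from the column it presumes faulty. It needs change, t and p to be wrong together yet in agreement, and the step result is borderline even then. A reader might also infer a bias towards VR, since all four printed changes favour VR more than the means do. If the post-test means are the misprint, the reported tests are not biased at all.

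**Conclusion.** The inconsistency is established for control left sit-and-reach and for step in both arms, and only marginally for VR left. Missing pairs are an unlikely explanation. Which column is wrong is not established, though the balance of evidence points to the post-test means; in that case the paired tests and the control-arm sentence stand.

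On the less likely reading, the unadjusted difference in change shrinks by about a third for left sit-and-reach (1.5/4.7) and about 14% for step (3.3/22.8). Both contrasts stay below 0.05 in rough checks. Control left improvement would be significant and control step borderline, provided the printed change SDs are correct. No direction of bias can be claimed until source data settle the matter. What is in doubt is the size of the effect and the control-arm statement, not necessarily the between-group significance.

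**What to change.** Check both endpoints against the raw score sheets. On one identical set of participants per arm, recompute the pre-test mean, post-test mean and paired change, and show n in each cell. Correct whichever column is wrong. Rerun the Table 5 tests and the Table 6 ANCOVA for these two endpoints, naming the test used for each row. Amend the control-group sentence in Chapter 4, Section 2, item 2 and the Abstract p-values only if the results change. Until then, do not cite the size of benefit on either endpoint.

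The cost is rechecking about 63 score sheets for two tests and rerunning existing analyses; no new data are needed. The drawback for the authors is that the stated benefit may shrink.

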The Effects of VR Interactive Games on Balance and Quality of Life Enhancement for Elderly in the Community

> Unique Protocol ID: N202210004 Document Date: June 26, 2023

Abstract

Thesis title: Examining the effectiveness of a virtual reality interactive game on physical fitness and quality of life in community-dwelling elderly people

Name of degree and program: Master's program in Long-term Care, Taipei Medical University

Graduate student: [name]

Thesis directed by: [name], Associate [name] Ph.D. Program in Gerontology and Long-term Care, Taipei Medical University

Background: Currently, community exercise courses are mostly guided by nurses and there are few opportunities for participating elderly people to interact with others during exercise. An interactive game was developed to allow elderly people participating in community activities to use game feedback to increase enjoyment and competitiveness in team games. Besides improving physical fitness, and increasing motivation and willingness to continue participating in exercise, this can also improve the quality of life.

Objective: To examine whether a virtual reality interactive game exercise can help improve the physical fitness and quality of life of elderly people. Methods: Elderly people aged 65 years and above who participate in community activities were recruited and randomized into the experimental group and control group. The experimental group completed 36 episodes of exercise intervention using the interactive game,

I

spread over 12 weeks, while the original routine exercise was used as the course content in the control group. Both groups underwent 36 episodes of intervention of one hour each time, thrice a week for 12 consecutive weeks. Assessments of functional physical fitness and satisfaction with quality of life were performed before and after intervention and the statistical significance was set as p < 0.05.

Results: After 36 weeks of virtual reality interactive game interaction, the post-test scores for 2-minute step test (p<0.001), right chair sit-and-reach test (p=0.010), left chair sit-and-reach test (p=0.002), psychological quality of life (p=0.033), and environmental quality of life (p=0.048) of the experimental group were all significantly higher than those of the control group.

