	protoct	posttast	difference	t value (p)	protost	nasttast	difference	t value (p)
	pretest	posttest	(Pre-test-P	或	pretest	posttest	(Pre-test-P	or
			ost-test)	S value (p)			ost-test)	S value (p)
	Mean ±	standard	deviation	-	Mean ±	standard	deviation	-
BMI	27.0 ± 3.5	26.9±3. 6	0.1±1.0	16.5 (0.741)	25.4 ± 3.8	25.3±3.7	0.1±0.4	75 (0.071)
30 seconds sit and stand	16.3±4.6	17.1±4. 4	-0.9±3.1	-56.5 (0.174)	17.7±5.2	18.5±4.9	-0.8±1.5	-83.5 (0.001)
The seat body bends forward (right)	96.0±20.7	121±25. 7	-26.6±31.2	-4.67(<0.001) §	92.5±25.4	98±20.2	-3.8±15.0	-1.47(0.151) §
The seat body bends forward (left)	2.9±10.1	7.3±9.6	-4.4±7.4	-140 (<0.001)	2.6±12.0	2.9±12.3	-0.3±2.8	0 (1.000)
Get up and walk Around at 2.4 meters	1.2±11.2	5.9±9.6	-4.9±8.1	-3.29 (0.003) §	1.4±13.4	2.9±13.2	-0.2±1.5	-0.79(0.433) §
Physiological quality of life	8.5±3.2	8.3±2.4	0.2±2.9	33 (0.507)	8.4±3.6	8.2±3.4	0.1±0.7	39 (0.384)
Psychological quality of life	10.8±1.4	11.1±1. 4	-0.1±0.4	-1.31 (0.202) §	11.4±1.5	11.3±1.4	0.0±0.1	1.00(0.325) §
Quality of social life	11.1±1.8	11.3±1. 7	-0.2±0.3	-18 (0.008)	11.7±1.8	11.7±1.9	-0.0±0.1	-0.5 (1.000)
Environment quality of life	11.2±1.9	11.3±1. 8	-0.1±0.4	-1.5 (0.500)	11.4±1.1	11.4±1.1	0.0±0.0	_*
The seat body bends forward (right)	10.6±2.2	10.6±2. 2	-0.0±0.1	-1.5 (0.500)	10.3±2.0	10.3±2.0	0.0±0.0	_*

§The Wilcoxon sign test is used, and the rest uses the dependent sample t test.

3. Comparison of Post-test between Experimental and Control Groups

Due to significant differences in demographic data and pre-test assessments between the experimental and control groups, particularly in the education level variable, and considering age as an important control variable, analysis of covariance (ANCOVA) was conducted to compare the post-test scores between the experimental and control groups. Age, education level, and pre-test scores were controlled for in the analysis. Intention-to-treat analysis was used.

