The results of ANCOVA analysis (Table 6) revealed that the post-test scores of the experimental group were significantly higher than those of the control group in five assessment outcomes, including the 2-minute step test (p < 0.001), right chair sit and reach (p = 0.010), left chair sit and reach (p = 0.002), psychological quality of life (p = 0.033), and environmental quality of life (p = 0.048). Additionally, the differences in fitness (except for the 30-second chair stand test) and quality of life had effect sizes (partial eta squared) ranging from 0.011 to 0.267, indicating moderate to substantial intervention effects. These results suggest that the intervention in this study was more effective in improving the aforementioned fitness and quality of life compared to regular community activities.

	StatisticsF /(p)	effect size (partial eta
		squared)
BMI	0.195 (0.661)	0.003
30 seconds sit and stand	0.015 (0.904)	0.000
The seat body bends forward (right)	21.154 (<0.001)	0.267
The seat body bends forward (left)	7.091 (0.010)	0.109
Get up and walk Around at 2.4 meters	10.294 (0.002)	0.151
Physiological quality of life	0.667 (0.418)	0.011
Psychological quality of life	0.956 (0.332)	0.016
Quality of social life	4.766 (0.033)	0.076
Environment quality of life	1.405 (0.241)	0.024
The seat body bends forward (right)	4.080 (0.048)	0.066

Table 6Post-test comparison between the experimental group and the

control group

Note: This analysis uses ANCOVA to control the pretest scores and other significant influencing factors

in the pretest. The control variables include: age, education level, and pretest scores of each variable.

Section 3: Analysis and Comparison of Quality of Life Questionnaire

Upon statistical analysis of pre-test and post-test scores (Table 7), it was found that in the experimental group, there was a difference of 0.4points in the physical domain (p = 0.202), no difference in the psychological domain (p = 0.008), a difference of 0.2 points in the social relationships domain (p = 0.500), and no difference in the environmental domain (p = 0.500). In contrast, in the control group, there was a difference of 0.4 points in the physical domain (p = 0.325), no difference in the psychological domain (p = 1.000), and no difference in the social relationships and environmental domains. The results indicate a significant change in the quality of life in the physical domain for the experimental group.

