Table 7 Analysis and comparison of pre- and post-test on the quality of life within the group after the experiment

		Test gro	up (N=30)			Control g	group (N=33)	
	pretest	posttest	score difference	t value (p)	pretest	posttest	score difference	t value (p)
		(Pre-tes	(Pre-test-	i value (p) prefess	pretest	lest positest	(Pre-test-	i value (p)
			Post-test)			Post-test)	_	
	Mean	\pm standard of	leviation	_	Mean	\pm standard	deviation	_
Physiological	10.0 + 1.4	11.1±1.4	0.1+0.4	-1.31	11 4 1 5	112114		1.00
quality of life	10.8±1.4 11	11.1±1.4	-0.1±0.4	(0.202)	11.4±1.3	11.3±1.4	0.0±0.0	(0.325)
Psychological	11 1 1 1 0	11.3±1.7	-0.2±0.3	-18	11 7 1 0	11.7±1.9	$0.0{\pm}0.0$	-0.5
quality of life	11.1±1.8	11.3±1.7	-0.2±0.3	(0.008)	11./±1.8	11./±1.9	0.0±0.0	(1.000)
Quality of	11.2+1.0	11 2 1 1 0	0.1 ± 0.4	-1.5	11 4 1 1 1	11 / 1 1 1		_*
social life	11.2±1.9	11.3±1.8	-0.1 ± 0.4	(0.500)	11.4±1.1	11.4±1.1	0.0 ± 0.0	_
Environment	10 (12 2	10 + 2 2	0.0 ± 0.1	-1.5	10.2 + 2.0	10.2 + 2.0		_*
quality of life	10.6±2.2	10.±2.2	0.0±0.1	(0.500)	10.3±2.0	10.3±2.0	0.0±0.0	_

*Since all subjects have the same score, the t test cannot be performed.

Chapter 5: Discussion

Section 1: Exploration of the Application of Virtual Reality Interactive Games in Community Care Centers

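### The environmental quality-of-life benefit (p = 0.048) rests on an ANCOVA with unplanned covariates, while apparently only 2 of 30 versus 0 of 33 participants changed at all

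*Combined protocol and SAP*

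**What the plan says.** - **Plan** (Chapter 3, Section 6, item 2(d)): "ANCOVA will be employed to compare the post-test scores between the experimental and control groups while controlling for pre-test scores". No other covariate is named.
- **Analysis reported** (Chapter 4, Section 2, item 3, and the note to Table 6): "The control variables include: age, education level, and pretest scores of each variable". The text explains that education differed between the arms and that age was considered important. No pre-test-only result is given.
- **Claim**: Chapter 4, Section 2, item 3 includes "environmental quality of life (p = 0.048" among the five significant ANCOVA results. The abstract says that the post-test scores for five outcomes, ending with "environmental quality of life (p=0.048) of the experimental group were all significantly higher than those of the control group". Chapter 5, Section 3 and Chapter 6 repeat the environmental benefit.
- **Effect size**: across outcomes, partial eta squared is described as "indicating moderate to substantial intervention effects".
- **Within-arm data** (Tables 5 and 7): the experimental arm's environmental score goes from 10.6 to 10.6 (Table 5), change 0.0±0.1, test entry -1.5 (0.500). The control arm's change is 0.0±0.0, and the Table 7 footnote says "Since all subjects have the same score, the t test cannot be performed".
- **Chapter 4, Section 3** reports no within-arm environmental difference (p = 0.500). It then concludes "The results indicate a significant change in the quality of life in the physical domain for the experimental group", although the p-value printed for that domain is 0.202.

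**The concern.** An outcome that did not move in any control and hardly moved in the experimental arm is reported as significantly better in the experimental arm. The result comes from a model with two covariates outside the plan, one of them added because of an observed baseline imbalance. The p-value only just passes 0.05, and the planned result is missing.

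Environmental quality of life is one of only two quality-of-life domains in the final conclusion. If the planned model does not support it, that conclusion narrows to the psychological domain. The covariates are disclosed, but nothing in the report shows what the planned model gives.

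**Working it through.** **1. Which Table 6 row is environmental.** The ten rows follow the order of Table 4, but the printed labels slip from the third row onward. In Table 4's order, rows 3, 4, 5, 8 and 10 carry exactly the p-values that the text gives for the step test, right and left sit-and-reach, psychological and environmental domains. The environmental result is therefore the last row: F = 4.080, p = 0.048, partial eta squared 0.066. The row labelled environment (1.405, p = 0.241) is the social domain.

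**2. Reproducing the printed result.** Partial eta squared = F/(F + df).

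| Model | Residual df | Partial eta squared |
|---|---|---|
| Intercept, group, pre-test, age, education (one linear term) | 63 − 5 = 58 | 4.080/62.080 = 0.0657 |
| Intercept, group, pre-test (planned) | 63 − 3 = 60 | 4.080/64.080 = 0.0637 |

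On 1 and 58 df, F = 4.080 gives p = 0.048. Only 58 df matches the printed 0.066, and the other significant rows imply 57.9 to 58.1 df. The printed result is thus arithmetically sound, and it comes from the expanded model fitted to the 63 completers.

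**3. How many participants changed.** The Table 5 footnote reads "The Wilcoxon sign test is used, and the rest uses the dependent sample t test" for its marked rows, which makes the unmarked environmental entry a t-test. But t = −1.5 on 29 df gives p = 0.144, not 0.500. The column header also allows an S value. For the signed-rank statistic, S = W⁺ − n(n+1)/4 over n non-zero changes. If all changes share a sign, |S| = n(n+1)/4 and the exact p = 2/2ⁿ.

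- n = 2: |S| = 1.5, p = 0.500, as printed.
- Enumerating n = 1 to 10 with every tie pattern gives no other solution.
- Other unmarked entries fit the same reading: S = −18 is n = 8, p = 2/256 = 0.008; S = −0.5 is n = 1, p = 1.000.
- The marked rows reproduce as t-tests: t = 1.00 on 32 df gives 0.325, and t = −3.29 on 29 df gives 0.003.

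The footnote therefore looks reversed. Changes are pre minus post, so the negative sign means that both participants rose. The inferred data are 2 of 30 against 0 of 33.

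**4. Size of the difference.** An experimental-arm mean change that rounds to 0.0 is below 0.05 in absolute value, and the control change is zero. Against a baseline SD of 2.0 to 2.2, this is below 0.05/2.0 = 0.025 SD. If two people changed and the SD of change lies between 0.05 and 0.15, the mean change is 0.010 to 0.039 points.

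**5. Unadjusted tests on 2/30 against 0/33.**

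- Fisher exact: p = 0.223.
- Pooled t-test on change, which does not depend on scale. With two equal changes of 1, the mean is 2/30 = 0.0667, the pooled variance (2 − 30 × 0.0667²)/61 = 0.0306, and the standard error √[0.0306 × (1/30 + 1/33)] = 0.0441. So t = 1.51, F = 2.28, p = 0.136.
- Equal changes are the most favourable case. If one change is half the other, F = 2.04, p = 0.158; if a tenth, F = 1.33, p = 0.253.

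These are not like for like with an adjusted F of 4.080, so the models themselves were simulated.

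**6. Simulation.** There were 20,000 data sets per case. Pre-test and age were drawn as independent normals with the published arm means and SDs. Education used the published counts as a linear score. Two experimental participants, chosen at random, improved.

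| Changes | Planned model, p ≤ 0.048 | Planned model, 5th–95th percentile of p | With age and education, p ≤ 0.048 |
|---|---|---|---|
| Equal | 0.62% | 0.086–0.216 | 3.5% |
| 2:1 | 0.37% | 0.101–0.250 | 2.3% |

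When each data set was forced to match the published arm means and SDs exactly, the planned model reached p ≤ 0.048 in essentially none (at most 1 in 20,000).

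**7. A comparison inside the report.** The social domain has the same within-arm pattern (−1.5, p = 0.500; all controls unchanged). Its ANCOVA p-value, with row order corrected, is 0.241.

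**The case against.** Adjusting for prognostic covariates is legitimate, and the report names them and says why they were used. The printed p-value is also correct for the model fitted. In the simulation even the expanded model misses p ≤ 0.048 in 96.5 to 97.7% of sets, so the published result is unusual under both models, which may mean that the simulation assumptions are wrong. The documents give no covariate correlations and do not say who changed.

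Table 5 is also not reliable throughout. It prints 10.8 to 11.1 with a change of −0.1, and 96.0 to 121 with a change of −26.6. The data behind the ANCOVA may not match the change column.

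Finally, a test of who changed cannot fall below (30 × 29)/(63 × 62) = 0.223 here, so that form of check would have a foregone result. The effect-size phrase describes a range across outcomes, not this domain alone.

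Much of this stands as a limit on certainty. It rules out saying that the planned model is known to be non-significant, and it is why the inference is stated as probable. It does not restore the claim. The environmental row of Table 5 is internally consistent, the near-zero change is printed, and a p-value of 0.048 is several times more likely with the added covariates than without. The Table 5 discrepancies are a further reason to check the data.

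**Conclusion.** The concern holds. The environmental benefit is not supported well enough for the abstract, discussion and conclusion. Three facts need no inference: the plan named the pre-test score as the only covariate, only an expanded model is reported, and the between-arm difference in mean change is below 0.05 points.

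That nominal significance probably depends on the added covariates rests on two further steps. One is reading the entry -1.5 (0.500) as a signed-rank result, which gives 2 of 30 changed. The other is the simulation's assumptions: independent normal covariates, linear education and randomly placed changers. The exact planned-model p-value needs the individual data. Confidence is medium. The matter should be corrected because it decides whether one or two quality-of-life domains can be claimed.

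**What to change.** 1. Report the planned pre-test-only ANCOVA as the main between-group analysis, and label the model with age and education as a sensitivity analysis.
2. For outcomes where most changes are zero, add a permutation or rank-based p-value.
3. State the number of participants who changed in each arm, and the mean difference with its confidence interval.
4. Remove environmental quality of life from the abstract, Chapter 5 and Chapter 6 unless the planned analysis supports it.
5. Correct the Chapter 4, Section 3 sentence on the physical domain: its within-arm p-value is 0.202, and the significant within-arm change was psychological (p = 0.008).
6. Correct the shifted row labels in Tables 5 and 6 and the test labels in Tables 5 and 7.
7. Check the post-test quality-of-life data against source, because all 33 controls show zero change in two domains.

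The cost is a re-run of one model with a permutation p-value on existing data, a source check, label corrections in three tables and possibly a narrower conclusion. No new data are needed.
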